14.3.14.2 Vital signs and physical examination

The change in vital signs (resting blood pressure, pulse, and body temperature) from baseline to each relevant visit will be summarized by treatment group as mean, standard deviation (SD), median, minimum and maximum values for the safety analysis set.

Subjects with abnormal, clinically significant physical findings will be listed. Furthermore, a shift table for physical findings showing the change from baseline to Week 16 in clinical assessments (normal; abnormal, not clinically significant; abnormal, clinically significant) will be performed.

14.3.14.3 Electrocardiography

Absolute values and change in ECG parameters (CCI [REDACTED]) from baseline to each relevant visit will be summarized by treatment group as mean, SD, median, minimum and maximum values for the safety analysis set.

Subjects with abnormal clinically significant ECG parameters will be listed. Furthermore, a shift table showing the change in clinical assessments (normal, abnormal not clinically significant, abnormal clinically significant) for the ECG parameters from baseline to Week 16 will be provided.

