^e The informed consent form must be signed prior to conducting any protocol-related assessments/procedures, including but not limited to screening evaluations and washout of disallowed medications. Screening evaluations may start later than the date when the informed consent form was signed.

^f At screening, the demographic data listed in Section 11.2.1 will be recorded. At baseline, only age will be recorded on the randomization form.

^g BSA affected by AD will be assessed as component A of SCORAD (Section 11.3.3).

^h If the results of the hepatitis B, C, HIV, and/or tuberculosis tests are inconclusive at screening, they may be repeated at an unscheduled visit, if necessary.

ⁱ At each visit between baseline and Week 14, the subject will self-administer the morning dose of IMP at the trial site under the supervision of the site staff.

^j Between visits from baseline to Week 16, the subject will self-administer the IMP at their home. The subject will take their last dose of IMP in the evening before the Week 16 visit.

^k ADSD, Nocturnal [REDACTED] Difficulty [REDACTED] Frequency of [REDACTED] During the Night, [REDACTED] and [REDACTED] will be completed in the eDiary daily.

^l Includes ADSD PGI-S, [REDACTED] PGI-S, Nocturnal [REDACTED] PGI-S, Difficulty [REDACTED] PGI-S, Frequency of [REDACTED] During the Night PGI-S, [REDACTED] PGI-S, and [REDACTED] PGI-S.

^m Includes ADSD PGI-C, [REDACTED] PGI-C, Nocturnal [REDACTED] PGI-C, Difficulty [REDACTED] PGI-C, Frequency of [REDACTED] During the Night PGI-C, [REDACTED] PGI-C, and [REDACTED] PGI-C.

ⁿ See Panel 3 for more information.

^o It will be at the discretion of the investigator if a urine sample should be sent to the central laboratory for further analysis.

^p Women of childbearing potential only.

^q Wristband actigraphy, skin biopsies, and exit interviews are optional components of the trial for subgroups of subjects. Participation in these components is not required for participation in the core part of the trial and the subject will be asked to provide additional consent.

^r At the indicated visits, subjects will be asked to bring the wristband actigraphy devices back to the site and the investigator or site staff will transfer data from the devices. Subjects will be asked to return the devices at Week 16 or at their last visit in the trial.

^s Skin biopsies should be taken from the locations described in Section 11.7.3.

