^t Exit interviews should be scheduled as described in Section 11.7.4.

Panel 3: Schedule of ECG measurements and PK blood samples in relation to fasting and administration of IMP

Week -5 (screening)	Week -1 (run-in)	Week 0 (baseline)	Week 1	Weeks 2, 6, 10, and 14	Weeks 4, 8, and 12	Week 16	Week 17 (safety follow-up)	Early termination	
NA	NA	Subject is fasted ^c					NA	NA	

 • 3 consecutive ECGs ^a • Laboratory assessments 	
 • 1 ECG ^b • Laboratory assessments 	
 • Pre-dose ECG ^d • Pre-dose PK ^e • Laboratory assessments 			
 • Pre-dose PK ^g • Laboratory assessments 	
 • 1 ECG ^b • 1 PK • Laboratory assessments 	
 • 1 ECG ^b • Laboratory assessments 	
 • 1 ECG ^b • 1 PK • Laboratory assessments 	
NA	NA	Administration of IMP Wait CCI and proceed with				Subject may break fast	NA	NA	
		
 • Post-dose ECG • Post-dose PK ^f 	
 • Post-dose ECG • Post-dose PK ^f 	
 • Post-dose ECG 	
 • Post-dose ECG • Post-dose PK ^f 				
NA	NA	Subject may break fast					NA	NA	NA
		
 • Japan: post-dose ECG (4 hours±15 min after dosing) ^h 	
 • Japan: post-dose ECG (4 hours±15 min after dosing) ^h 						

Abbreviations: ECG = electrocardiogram; IMP = investigational medicinal product; NA = not applicable, PK = pharmacokinetic(s).

If at any ECG measurement, the subject presents with a **CCI**, the ECG should be repeated. If the **CCI** is confirmed, a PK sample (if not already planned at the visit) must be taken close to the last ECG. See Section 11.4.3 for more information.

THIS DOCUMENT CONTAINS CONFIDENTIAL INFORMATION AND MUST NOT BE COPIED OR MADE AVAILABLE TO ANY THIRD PARTY WITHOUT THE PRIOR WRITTEN CONSENT OF THE LEO PHARMA GROUP

- ^a In line with exclusion criterion 13. Must be measured before any blood sample collected at the same visit.
- ^b Must be measured before any blood sample collected at the same visit.
- ^c The subject will be asked to come fasted to the trial site, i.e. arrive at the site minimum 2 hours after their last meal.

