10.3 Early termination assessments

Assessments/procedures to be conducted at the visits below are listed in the schedule of trial procedures (Section [4](#)).

Permanent discontinuation of IMP

Subjects who permanently discontinue IMP prior to Week 16 will be asked to attend:

- An early termination visit as soon as possible after last dose of IMP.
- The primary endpoint visit (nominal), 16 weeks after first dose of IMP.

See also Section 10.4 for the continued assessment of discontinued subjects.

Withdrawal from trial

Subjects who withdraw from the trial prior to randomization will be considered screening failures

Subjects who withdraw from trial after randomization will be asked to attend:

- An early termination visit as soon as possible after last dose of IMP.
- A safety follow-up visit (7 days after last dose of IMP).

A subject, who at the earliest can come to the early termination visit 3 days after last dose of IMP or later, should only be asked to attend the early termination visit.

If the subject agrees, the investigator will review any AEs which will be followed up as described in Section 13.7.

10.4 Continued assessment of subjects after permanent discontinuation of investigational medicinal product

Subjects who permanently discontinue IMP prior to Week 16 should be encouraged to continue participating in the trial and to follow their visit schedule to the extent possible.

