The collection and transmission of ECG data will be described in a separate ECG manual.

Reporting in eCRF

It must be recorded in the eCRF if an ECG was measured. If not, a reason must be provided. It will also be recorded if the subject was fasted (i.e. had arrived at the trial site minimum 2 hours after their last meal). The investigator's evaluation of ECG result (normal, abnormal not clinically significant, abnormal clinically significant) must also be recorded.

Before first dose of IMP, any abnormal clinically significant or clinically relevant ECG finding will be documented as medical history in the eCRF. After first dose of IMP, any new abnormal clinically significant or clinically relevant ECG finding, symptoms, or illnesses, as well as any clinically significant deterioration of a pre-existing condition will be reported as an AE as described in [Section 13.3](#).

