12.2 Appropriateness of assessments

All trial assessments and procedures are listed in the schedule of trial procedures (Section 4).

Efficacy assessments

EASI, vIGA-AD, and SCORAD are validated measures used in clinical practice and/or clinical trials by investigators to assess the severity and extend of AD (Sections 11.3.1 to 11.3.3). SCORAD additionally assesses subjective symptoms.

ADSD is a validated diary developed by LEO Pharma for subjects to assess the severity of 9 key signs and symptoms of AD (Section 11.3.4).

PROs

A range of validated PROs will be used to assess subject perception of AD. The PROs have been selected to cover key signs and symptoms of AD (including CCI as well as health-related quality of life (including CCI quality and impact of CCI on sleep quality), mental health, and work productivity (Sections 11.5.7 to 11.5.13). The PROs are scheduled in a combination to balance the time spent by the subject on these questionnaires at the trial site and daily in the eDiary.

Safety assessments

Standard clinical methods of subject evaluations, such as AE monitoring (Section 13), vital signs, physical examinations, ECG, laboratory testing including pregnancy testing (Section 11.4) will be used to assess subject safety.

Due to the important potential risk of CCI, subjects' ECGs will be monitored as described in Section 11.4.3 and the ECG endpoints will be used to assess effect of treatment on CCI.

An independent DMC will review all safety data and monitor the overall conduct of the trial periodically (Appendix 3H).

Pharmacokinetic assessments

Plasma concentration of LEO 152020 (C_{trough} and C_{max}) will be measured pre- and/or post-dose of IMP and PK parameters will be derived to explore the exposure-response relationship of LEO 152020 (Section 11.6).

Based on data from the first-in-human trial with LEO 152020 (39), C_{max} is expected to occur at [CCI]. Therefore, post-dose PK blood samples will be collected shortly after the post-dose ECG measurement (see Panel 3 for more information).

Pharmacodynamics assessments

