Electrocardiogram CCI [REDACTED]	This AESI was defined based on data from the first-in-human trial with LEO 152020 (39)	
 • ECG (measured according to the schedule of trial procedures [Section 4]). • Severity of the CCI [REDACTED] (mild, moderate, severe, see QTcF severity criteria in Panel 14). • Symptoms believed to be related to the CCI [REDACTED] and duration of the symptoms. 	eCRF

Abbreviations: AD = atopic dermatitis; AESI = adverse event of special interest; ECG = electrocardiogram; eCRF = electronic case report form; PCR = polymerase chain reaction (test); CCI [REDACTED]

AESIs of electrocardiogram QT corrected interval prolonged

QTcF >450 ms (men) and QTcF >460 ms (women) are considered clinically relevant QT prolongations and must be reported as AEs. QTcF severity of the AE must be recorded in the eCRF (see Panel 14 for guidance). For guidance on handling events of QT prolongation, see Section 11.4.3.

Panel 14: Severity specifications for adverse event of electrocardiogram CCI [REDACTED]

Mild	Moderate	Severe
Men: 450 ms < average CCI [REDACTED] ≤ 480 ms Women: 460 ms < average CCI [REDACTED] ≤ 480 ms	480 ms < average CCI [REDACTED] ≤ 500 ms or 30 ms < increase in CCI [REDACTED] from baseline ≤ 60 ms	Average QTcF > 500 ms or Increase in QTcF from baseline > 60 ms

Abbreviations: CCI [REDACTED]

^a Modified from (62) in line with the CCI [REDACTED] guideline on clinical evaluation of CCI (34).

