14.3 Statistical analysis

14.3.1 General principles

All significance tests will be two-sided using the 5% significance level. All confidence intervals will be presented with 95% degree of confidence, unless otherwise specified. Efficacy analyses will be based on the FAS, and safety analyses will be based on the SAF.

If not mentioned otherwise, endpoints will be summarized descriptively at each relevant visit by treatment group. For endpoints evaluated over time, plots will be made to explore the trajectory with time.

An observed-cases approach will be used for tabulations of data by visit (i.e. involving only those subjects for whom data was collected at each specific visit). The number of subjects for whom data was not collected at each specific visit will also be provided.

Categorical data will be summarized by treatment group, using the number and percentage of subjects in each category. Continuous data will be summarized using the mean, median, SD, 1st quartile, 3rd quartile, minimum and maximum values. Additionally, the geometric mean and coefficient of variation (CV) will be provided for PK endpoints.

In general, for endpoints evaluated as the change from baseline and/or where a baseline adjustment is applied, baseline is defined as the assessment conducted at the randomization visit (Visit 3) if not otherwise stated.

All the analyses specified in the protocol will be reviewed in relation to the blinded data actually obtained, and the statistical analysis plan will be finalized before breaking the randomization code.

Any changes from the statistical analyses planned in this CTP will be described and justified in a protocol amendment, the statistical analysis plan and/or in the CTR, dependent on the type of change.

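### The only ECG shift table runs from baseline to Week 16 and uses none of the post-dose ECGs, so it tends to understate on-drug shifts in ECG rating

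*Combined protocol and SAP*

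**What the plan says.** Section 14.3.14.3 names three ECG outputs on the safety analysis set: by-visit summaries of values and changes, a listing of subjects with clinically significant abnormal ECGs, and one shift table of the three-category rating that "for the ECG parameters from baseline to Week 16 will be provided".

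The ECG timetable is in Section 4, Panel 3 ("Schedule of ECG measurements and PK blood samples in relation to fasting and administration of IMP"). It has a post-dose ECG at baseline and at every visit to Week 14, then one ECG at Week 16 and one at Week 17. Panel 2, footnote j, settles dosing at Week 16: "The subject will take their last dose of IMP in the evening before the Week 16 visit". Section 11.6.1 puts the post-dose ECG at 1 hour, give or take 15 minutes. Section 12.2 explains, from the expected time of Cmax, why "post-dose PK blood samples will be collected shortly after the post-dose ECG measurement".

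Three further provisions bear on the table:

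- **Rating.** Section 11.4.3 says that the investigator's "evaluation of ECG result (normal, abnormal not clinically significant, abnormal clinically significant) must also be recorded", and does not limit this to particular visits.
- **Baseline.** Section 14.3.1 says "baseline is defined as the assessment conducted at the randomization visit (Visit 3) if not otherwise stated". Visit 3 has both a pre-dose and a post-dose ECG.
- **Stopped subjects.** Section 10.3 asks subjects who discontinue IMP early to attend "The primary endpoint visit (nominal), 16 weeks after first dose of IMP".

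**The concern.** Section 5.5 treats an ECG-related effect as an important potential risk, and Section 12.1 refers to mitigating QT prolongation. Section 5.5 also says that paired ECG and PK samples will be used to explore whether exposure drives the effect. If it does, the informative ECGs are those taken near peak concentration. The shift table is the one display that counts, by arm, how many subjects moved from a normal to an abnormal rating, and it uses none of those ECGs.

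It also has no on-treatment limit. The safety analysis set is everyone exposed to IMP, so a subject who stopped weeks earlier and attends the nominal visit is tabulated off drug. A subject with no Week 16 ECG contributes no category under the observed-cases rule in Section 14.3.1, even if an earlier on-drug or early-termination ECG was abnormal. An active arm could look like placebo in this table although post-dose ratings differed.

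**Working it through.** The plan gives no figure to reproduce here. The check is a count from Panel 3, a comparison of outputs, and a small illustration.

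**1. Count of ECG visits after first dose (Panel 3)**

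- Visits with a post-dose ECG: Week 0 (1) + Week 1 (1) + Weeks 2, 6, 10, 14 (4) + Weeks 4, 8, 12 (3) = 9.
- Other scheduled visits with an ECG after first dose: Week 16 and Week 17 = 2.
- Total 9 + 2 = 11. The shift table uses 1 of 11 visits and 0 of 9 post-dose ECG visits. (Japan has an extra 4-hour ECG at Weeks 0 and 1, which adds time points but no visits.)
- Visits with a paired post-dose PK sample: Weeks 0, 1, 4, 8, 12 = 5 of 9. Weeks 2, 6, 10 and 14 have the ECG only.

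**2. What the Week 16 ECG measures**

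- Still on IMP: last dose the evening before, so about one dosing interval later. The regimens are redacted, so the time since the last active tablet cannot be stated by arm.
- Stopped IMP: off drug.

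**3. What each planned output shows**

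| Output | On-drug ECGs included? | By-arm count of on-drug rating shifts? |
|---|---|---|
| Shift table (14.3.14.3) | Week 16 only, not post-dose | No |
| By-visit summaries with maxima (14.3.14.3) | Yes | No; a maximum is one extreme value |
| Listing (14.3.14.3) | Yes, if clinically significant | No; omits lesser abnormalities |
| AESI tables (13.6.1, 14.3.14.1) | Yes, if reported as an AE | Event counts only |

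What none of them gives is by-arm counts of on-drug shifts in category, mainly to abnormal but not clinically significant.

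**4. QTcF rises of 30 to 60 ms**

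Section 13.6.1 says that QTcF above 450 ms (men) or 460 ms (women) "are considered clinically relevant QT prolongations and must be reported as AEs". Panel 14 grades a rise of more than 30 and up to 60 ms as moderate whatever the absolute value, and Section 11.4.3 requires a repeat ECG and a PK sample for it. Section 11.4.3 also requires clinically relevant new findings to be reported as AEs. The text does not settle whether such a rise with QTcF at or below 450/460 ms is itself an AESI.

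**5. Illustration (every rate assumed; the documents give none)**

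Arm size 224 × 4/14 = 64. Assume a 5% chance of an abnormal rating at one post-dose ECG and 1% off drug.

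- One post-dose visit: 64 × 0.05 = 3.2 subjects.
- Week 16, nobody stopped, risk 25% to 100% of the post-dose risk: 64 × 0.0125 = 0.8 to 64 × 0.05 = 3.2.
- Week 16, 30% stopped: 64 × (0.7 × 0.0125 + 0.3 × 0.01) = 0.75 to 64 × (0.7 × 0.05 + 0.3 × 0.01) = 2.4.
- Worst of nine: 3.2 if the readings are fully dependent, 64 × (1 − 0.95^9) = 23.7 if independent.
- Worst of nine at the 1% rate (as on placebo): 0.64 to 64 × (1 − 0.99^9) = 5.5.

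Like for like, one look against one look, Week 16 shows at most as many shifts as a post-dose visit. The two are equal only if the risk is unchanged at Week 16 and nobody has stopped. Any increase from one post-dose look to the worst of nine comes from the number of looks, not from timing.

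**The case against.** The strongest reply is that little is lost. Values and changes are summarized at each relevant visit with maxima, and the listing is not tied to Week 16. QT prolongation is an AESI tabulated by arm and reviewed by the DMC, and QTcF above 500 ms or a rise above 60 ms stops IMP. Week 16 is the end-of-treatment visit, and the physical-findings table in Section 14.3.14.2 has the same form. The amendment history (Appendix 10) says that ECG parameters were removed as endpoints because a dedicated trial is planned. Baseline and window details are often left to the SAP, which Section 14.3.1 says is finalized before unblinding.

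Most of this stands, and it fixes the size of the point. It does not remove it. The same amendment kept the ECG assessments and added Section 14.3.14.3 to present them, and Section 12.2 still says that ECG data will be used to assess a treatment effect. Section 14.3.14.3 states a time point for the table, so this is a chosen rule and not merely a detail left open.

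Three stronger inferences are not supported:

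- That a QT signal would go unreported. The other outputs carry on-drug data.
- That rises of 30 to 60 ms below 450/460 ms are certain to be uncounted. The reporting trigger is ambiguous.
- That Week 16 is drug-free. It is not for subjects still taking IMP.

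**Conclusion.** The point holds as a minor one. The only ECG shift table is placed at a visit with no dose, has no on-treatment limit, and leaves out the post-dose ECGs from nine visits. It therefore tends to understate on-drug shifts. The loss is confined to by-arm counts of category shifts on drug. No endpoint, decision rule or subject protection is affected.

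The direction rests on the reasonable assumption that any ECG effect follows concentration, and on the fact that stopped subjects are invited to Week 16. The size cannot be derived: abnormality rates are not given, and the half-life and ECG effect sizes are not available in the public text. The counts in the illustration are not estimates for this trial. The visit counts depend on Panel 3 as extracted, but they agree with the schedule in Panel 2 and the dosing footnotes. If the final SAP already contains a worst-on-treatment ECG table, the point falls away.

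**What to change.** In Section 14.3.14.3 or the SAP, before unblinding:

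1. State that the pre-dose ECG at Visit 3 is the ECG baseline.
2. Keep the Week 16 table. Add a shift table by arm, placebo included, from that baseline to the worst rating on IMP up to 3 days after last dose (the treatment-emergent window in Section 14.3.14.1). Include post-dose, unscheduled and early-termination ECGs.
3. Over the same window, give by-arm counts of subjects whose measured QTcF crosses the Panel 14 thresholds, for absolute value and for increase from baseline. This gives those counts however the AESI wording is read.

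The cost is plan wording and two extra tables. No new ECGs, samples or visits are needed. Worst-value counts rise by chance in every arm, and subjects with unscheduled ECGs have more chances of an abnormal reading, so both tables must be read against placebo.

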14.3.14.4 Clinical laboratory evaluation

The change in each of the laboratory parameters from baseline to each relevant visit will be summarized by treatment group as mean, SD, median, minimum and maximum values for the safety analysis set.

Laboratory parameters will be classified as 'low', 'normal', or 'high', depending on whether the value is below, within, or above the reference range, respectively. A shift table will be produced showing the categories at baseline against those at the end of treatment. Subjects with laboratory parameters outside the reference range will be listed.

14.3.15 Pharmacokinetic analysis

The PK endpoint

- C_{trough} of LEO 152020 at Weeks CCI [REDACTED]
- C_{max} of LEO 152020 at Weeks CCI [REDACTED].

will be summarized for subjects in the PK analysis set and with PK assessments at the relevant visits using geometric mean, coefficient of variation (derived based on a log-normal distribution assumption), median, 1st quartile, 3rd quartile, minimum and maximum values.

Appendix 1: Definitions of adverse events and serious adverse events

Adverse event definition

An AE is defined as any untoward medical occurrence in a patient or clinical investigation subject administered a pharmaceutical product and which does not necessarily have a causal relationship with this treatment. An AE can therefore be any unfavorable and unintended sign (including an abnormal laboratory finding), symptom, or disease temporally associated with the use of a medicinal (investigational) product, whether or not related to the medicinal (investigational) product (69).

This definition includes:

- Accidental injuries.
- Events related to trial procedures.
- Reasons for any unfavorable and unplanned change in medication (drug and/or dose).
- Clinically significant worsening of pre-existing conditions.
- Reasons for admission to hospital or surgical procedures*.
- AEs commonly observed and AEs anticipated based on the pharmacological effect of the IMP.
- Any laboratory abnormality assessed as clinically significant by the investigator (see Section 11.4.4.2).

Serious adverse event definition

An SAE is any untoward medical occurrence that:

- Results in death.
- Is life-threatening – at risk of death at the time of the SAE (not an event that hypothetically might have caused death if more severe).
- Requires inpatient hospitalization or prolongation of existing hospitalization*.
- Results in persistent or significant disability or incapacity.
- Is a congenital anomaly or birth defect.

- Is a medically important condition. Events that may not be immediately life-threatening or result in death or hospitalization but may jeopardize the subject or may require intervention to prevent one of the other outcomes listed in the definition above. Examples are intensive treatment in an emergency room or at home for allergic bronchospasm, blood dyscrasias, and convulsions that do not result in hospitalization, development of drug dependency, or drug abuse.

Additionally, all malignancies, including skin malignancies, should be reported as SAEs.

*Hospitalization for procedures or treatments planned prior to the subject consented to trial participation does not constitute an AE and should therefore not be reported as AE or SAE.

Hospitalization for elective treatment of a pre-existing condition which did not worsen from the subject consented to trial participation is not considered an AE and should therefore not be reported as AE or SAE, even if not planned before consent to trial participation.

Hospitalization for routine scheduled treatment or monitoring not associated with any aggravation of the condition does not constitute an AE and should therefore not be reported as AE or SAE.

Hospitalization for administrative purpose does not constitute an AE and should therefore not be reported as AE or SAE.

Complications that occur during hospitalization are AEs. If a complication prolongs hospitalization, the event is an SAE.

When in doubt as to whether hospitalization occurred, the AE should be considered serious.

Adverse events of special interest definition

An AESI (serious or non-serious) is an event type of scientific and medical concerns specific to the product or development program, for which additional monitoring may be appropriate. Such an event may warrant further investigation in order to characterize and understand it. Depending on the nature of the event, rapid communication by the investigator to the sponsor and/or from the sponsor to other parties (e.g. regulators) may also be warranted.

AEs considered AESIs in this trial are described in Section [13.6.1](#).

